## *Inclusion/Exclusion Criteria*

### ***Inclusion Criteria***

- Staff (e.g., physicians, nurses, front desk) at the outpatient hematology sites who are able to converse in English or Spanish, and are 18 years of age or older.
- English- or Spanish-speaking parents and caregivers of children with SCA aged 0-12 who receive care at one of the four study sites and take daily penicillin or hydroxyurea.

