### ***Definition of Primary and Secondary Outcomes/Endpoints***

Because qualitative research is by nature exploratory, we have not defined outcomes for the focus group discussions with practice staff (**Aim 1**); however, we will use the Promoting Action on Research Implementation in Health Services (PARIHS) framework to guide these discussions about facilitators and barriers to WE CARE implementation. Key areas of exploration will be (1) evidence: attitudes and beliefs about evidence of the WE CARE system; (2) context: organizational, systemic, and sociopolitical features that promote or hinder implementation of WE CARE; and (3) facilitation: attributes of the facilitation that supported or impeded the implementation, and needed adaptations.

Primary outcomes for **Aim 2** include the following:

- *Identification of unmet needs and provision of referrals.* Previously utilized forms will be used during baseline and follow-up questionnaires to measure whether practitioners provided families resource handouts.
- *Parental enrollment in community-based resources.* Baseline and follow-up questionnaires to measure enrollment in community resources.
- *Process measures.* Data will be collected on adherence to clinic visits (appointments kept, cancelled, and no-show). We will collect data on medications adherence in two ways. First, we will collect laboratory markers that are commonly affected by HU, including hemoglobin and hemoglobin F levels, white blood cell and absolute neutrophil counts, and MCV. We will also collect data on prescriptions written and filled for HU and penicillin through EHR review and parent report.
- *Health outcomes:* Data on vaso-occlusive episodes, acute chest syndrome and sepsis will be collected from the EHR at 6-month- and 12-month follow-up. Quality of life will also be assessed through both the PedsQL, which has been validated in children with sickle cell disease and is responsive to change, and the PedsQL Sickle Cell Disease Module.
- *Healthcare utilization outcomes:* Data on emergency department visits, hospitalizations, and clinic visits will be collected from the EHR at baseline and 12-month follow-up. We have chosen

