*\*Research Electronic Data Capture (REDCap) is a research focused, electronic web-based data capture system. REDCap is a data collection tool and allows for storage and management of both surveys and databases. REDCap is a secure storage system and meets HIPAA compliance standards. REDCap software will be used to facilitate parent consents, questionnaires, and forms.*

**Materials.** The research data will include questionnaires completed by parents/caregivers both in-person and via telephone, parent hair cortisol samples, and medical chart review. Only trained project staff at each clinical site will have access to participants' identifying information.

For the hair cortisol samples, we will be following the hair collection protocol developed by [name] from the University of Massachusetts (UMASS). Hair will be cut at the level of the scalp from 2-3 locations and cut to 3cm at the distal end. Hair samples will be placed directly into a plastic vial; each vial will be labeled by an ID number uniquely linked to each study subject (see below). Hair cortisol is stable at room temperature indefinitely, thus vials will be stored in a locked file cabinet.

For the *medical chart review*, existing trained research staff members at each study site, will collect the data. We decided to use existing research staff for the data collection component of the study since getting chart review credentialing is difficult at each of the study sites. At baseline and 12-month follow-up, medical charts will be reviewed in order to determine the number of appointments kept versus cancelled or no-show, the number of days covered by prescription refills for penicillin and hydroxyurea, and blood tests for monitoring hydroxyurea (including WBC, HB F%, and MCV). At 6-month and 12-month follow-up, medical charts will be reviewed in order to determine the frequency of vaso-occlusive episodes, acute chest syndrome, and sepsis diagnoses.

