***Aim 2. Obtain population-specific empirical estimates of study parameters to plan a pragmatic large-scale cluster RCT.*** We will summarize the number of parents contacted, lost to follow-up, refusing participation, and enrolled. We will examine this by gender (e.g., father vs. mother). We will note reasons for refusals. We will determine parents' recruitment and attrition rates and receipt of WE CARE using descriptive statistics. We will also determine the data collection completion rate, including hair cortisol, for each data time point (baseline, 3-, 6-, 9-, and 12-month follow-up) via descriptive statistics. Each outcome and process variable described above will be first transformed into its final composite value/score. We will calculate within-group mean and standard deviation of our SDoH, process, mediator and health utilization and health outcome variables. We will also break down the intervention group into two subgroups differentiated by whether parents enrolled in resources at follow-up, and explore any differences. An intention-to-treat approach will be used to explore differences between the intervention and control groups. We will also report all data disaggregated by gender. Two independent sample t-test and chi-square tests will be used to determine bivariate differences. Mixed effects regression models will be used to estimate the effect size of the intervention on SCA outcomes accounting for baseline differences in sociodemographics, types of SDoH, cumulative needs, receipt of services, and *a priori* determined covariates (i.e. sociodemographic characteristics). To explore potential moderators for the intervention effect at the parent, child and family levels (e.g., gender, race, ethnicity, age, language, household income), we will use Rothman's methodology; specifically, we will conduct stratified analyses for each potential moderator followed by using standard interaction terms in our models. We will also explore mediation of our hypothesized potential mediators between SDoH and the intervention with each SCA health outcome using the approach recommended by MacKinnon, Lockwood, and Williams. We will account for the clustering by study site by calculating the intraclass correlation.

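### Baseline hydroxyurea use is left out of the Aim 2 covariates, and the hydroxyurea laboratory markers have no on-treatment denominator

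*Combined protocol and SAP*

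**What the plan says.** Either drug qualifies a child: the Inclusion Criteria ask that the child "take daily penicillin or hydroxyurea". Background and Significance introduces HU and antibiotic prophylaxis together and refers to them as therapies proven effective in sickle cell anemia.

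Under Data Collection Methods (Study 2, medical chart review), charts are reviewed at baseline and 12 months for "the number of days covered by prescription refills for penicillin and hydroxyurea" and for "blood tests for monitoring hydroxyurea (including WBC, HB F%, and MCV". Under Definition of Primary and Secondary Outcomes/Endpoints, medication adherence is measured in two ways. The first is laboratory: "we will collect laboratory markers that are commonly affected by HU". The second is prescriptions written and filled.

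The Data Analysis Plan (Aim 2) fits mixed models "accounting for baseline differences in sociodemographics, types of SDoH, cumulative needs, receipt of services", plus a priori "determined covariates (i.e. sociodemographic characteristics". It also states: "Two independent sample t-test and chi-square tests will be used to determine bivariate differences". Neither the covariates nor the example moderators include a treatment or disease variable.

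Study Design (Study 2) fixes two sites per arm and allocates them by uniform random numbers, without balancing on HU use. The description of study treatments says families are enrolled once WE CARE is fully running. Statistical Power and Sample Considerations says the pilot will not be used to judge efficacy, and that control-group estimates will feed the power calculations of a later trial.

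**The concern.** There are two separate issues.

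**Effect estimates.** If HU reduces acute events, as the background implies, the share of children on HU in each arm affects ED visits, vaso-occlusive episodes and acute chest syndrome whatever WE CARE does. With four sites that share need not balance, and the planned model has no term that would remove the difference.

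**Laboratory adherence measure.** In a child who takes only penicillin, hemoglobin F, MCV and the blood counts say nothing about adherence to HU. Pooling children on and off HU turns a measure of adherence into one that depends largely on who is prescribed the drug. This does not require any imbalance between arms. It affects the output that the pilot says it exists to deliver, the control-group planning values.

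**Working it through.** **1. Collected against used.** HU refill days and HU blood tests are collected at baseline, so HU status can be derived from data already planned. It appears nowhere in the adjustment set, and no sentence sets a denominator for the laboratory markers.

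**2. Yardstick from the plan.** The plan states more than 90% power for a 25-point difference in the proportion with an ED visit. Inputs: 2 × 35 = 70 children per arm, control rate 80%, so 80% against 55%, alpha 5% (sidedness not stated).
- Normal approximation, no clustering: 89.3% two-sided, 94.2% one-sided.
- With the plan's own cluster coefficient of 0.01: design effect 1 + (35 − 1) × 0.01 = 1.34, effective n = 70/1.34 = 52.2 per arm, power 78.7% two-sided, 86.9% one-sided.

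The stated figure is thus reached, or nearly so, only without the design effect. The present point does not depend on that; the 25 points serve only as a scale.

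**3. Shift from unequal HU share, with no WE CARE effect.** An arm mean is p × (mean on HU) + (1 − p) × (mean off HU), so

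shift = (difference in HU share) × (on/off-HU difference in outcome).

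Both factors are assumptions, because the documents give neither.

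| HU share difference | ED-visit risk difference on/off HU | Shift |
|---|---|---|
| 10 points | 10 points | 1 point |
| 20 points | 20 points | 4 points |
| 20 points | 25 points | 5 points |
| 40 points | 30 points | 12 points |

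Rejection rate of an individual-level two-sided 5% test, given that imbalance, with control rate 80%:
- Middle case, 80% against 76%: 8.8% at n = 70, 7.8% at n = 52.2.
- Largest case, 80% against 68%: 36.5% and 28.6%.
- Smallest case: about 5%.

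**4. How likely is such an imbalance?** If site HU shares vary with standard deviation s, the arm difference has SD √(s² + 2 × 0.25/70), taking an average share of one half. The chance of an arm difference of at least 20 points is 4.2%, 12.7%, 24.5% and 35.7% for s = 5, 10, 15 and 20 points. The value of s is again assumed.

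**5. Laboratory markers, unequal share.** In units of the SD within the on-HU and off-HU groups, gaps of 0.5 to 1.5 SD and share differences of 10 to 40 points give shifts of 0.05 to 0.60 SD. In the middle case (gap 1 SD, 20 points) the shift is 0.2 SD. The pooled SD is √(1 + 0.24) = 1.114, and the rejection rate is 18.6% at n = 70 and 15.1% at n = 52.2.

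**6. Laboratory markers, equal share.** With half the children on HU and a gap of d SD, the pooled variance is 1 + 0.25d². For d = 1 it is 1.25, and for d = 1.5 it is 1.56. A later trial sized on that SD for a fixed absolute difference would be 25% to 56% larger than one sized on children on HU. The control mean would move with the HU share as well.

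**The case against.** The strongest reply is that this is a pilot that disclaims efficacy, and that any imbalance would arise by chance. Both statements are true. A reader might infer that the omission biases the trial systematically. It does not: over repeated allocation the expected imbalance is zero, and with only six possible allocations HU is one of many site factors that could differ. However, the plan still estimates an intervention effect size and applies individual-level t and chi-square tests, which make no allowance for site-level imbalance.

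Other points stand in part:
- **Age as a proxy.** If age counts as sociodemographic, it captures some of the therapy difference, since the background describes antibiotic prophylaxis to age 5. It also says HU should be offered from 9 months, so age does not identify who is on it.
- **Baseline ED visits.** These are collected and could absorb part of a pre-existing HU difference, but the plan does not list them as a covariate.
- **Control ED-visit rate.** A rate in the mixed eligible population is a legitimate planning value. The criticism of control-group means and SDs is confined to the laboratory markers.
- **Prescription is not exposure.** The background cites a Medicaid study in which 41% of children prescribed HU were adherent, so a yes/no covariate is coarse.
- **Marker wording.** The plan calls the markers affected by HU and describes them as HU monitoring tests. It does not say that penicillin-only children will be scored for HU adherence. The fault is a missing rule, not a stated wrong one.

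**Conclusion.** The point holds as a should-fix item for an exploratory analysis. A prognostic treatment variable that can be derived from planned baseline data is left out of the model, and the laboratory adherence measure lacks a denominator.

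The size for ED visits is unknown from the documents. Under the assumed inputs it is roughly 1 to 12 points, with 4 to 5 in middle cases, below the 25-point planning difference throughout. The laboratory issue is the firmer of the two because it needs no imbalance. Its 1.25- to 1.56-fold variance figures assume half the children on HU and a gap of 1 to 1.5 SD.

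Two further inferences go beyond the text. One is that HU prescribing differs between these sites: no site shares are given. The other is that HU status is already recorded for every child: qualifying on penicillin does not reveal it, and the chart review records refill days and blood tests, not a dated HU-status field.

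**What to change.** 1. In the Data Analysis Plan (Aim 2), add HU prescribed at baseline (yes/no) as an a priori covariate for ED visits and sickle cell health outcomes. Derive it from the baseline chart review by one written rule applied identically in both arms. Because enrolment follows implementation, baseline status at WE CARE sites may already have been affected. Repeat the analysis with status before launch where the EHR shows it. This should be a sensitivity analysis only: the Study Timeline shows about five quarters of accrual, so launch-date status could be more than a year old for late enrolees. Do not adjust for HU use during follow-up, which may lie on the causal path.
2. In the endpoint definitions and the Data Analysis Plan, define the laboratory adherence measure only for children prescribed HU at that same baseline date, not at follow-up, so that the subset is not selected on later prescribing. Report 12-month values with and without adjustment for the baseline laboratory value, since a baseline taken after implementation may carry part of any effect.
3. Report HU share by site and arm.

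**Cost.** SAP wording, one derived chart-review variable and, where available, a look-back in the EHR. The laboratory analysis will rest on fewer children and the model gains a term. Some effect may be absorbed if WE CARE had already changed baseline HU status. Other site-level differences remain with four sites.

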## Statistical Power and Sample Considerations

We will enroll up to 235 subjects in this study, including up to 60 practice staff and 175 parents of children with SCA.

Because the goal for **Aim 1** is to examine the implementation of WE CARE in the outpatient pediatric hematology clinical setting our sampling will be purposeful. Based on our previous experience, we anticipate up to 15 practice staff per site will participate in focus group discussions.

For **Aim 2**, we are proposing to enroll 35 families from each of the four study sites (2 experimental, 2 control) to field test study logistics, including collecting empiric estimates of study parameters for a larger pragmatic trial. To demonstrate the feasibility of our study design, we use ED visits (primary

outcome) and penicillin adherence as examples. Assuming a 5% error rate, and based on our R00 WE CARE study, we expect a cluster coefficient no larger than 0.01. Based on recent data, we expect at least 80% of children in our control group to have at least one ED visit within our study observation period. We expect that our intervention group will have a much lower proportion, with ≤40% having with one or more ED visits. Our proposed study sample has >90% power to detect differences of at least 25% in the proportion of children with ED visits. In addition, based on estimates from the literature we expect a 9-month medication adherence of 40% and 10% in the intervention and control groups, respectively. Our study will have 90% power to detect differences of at least 20% in penicillin adherence, which is considered clinically significant. Consistent with CONSORT guidelines for pilot studies, we will not use results from this study to determine efficacy, since effects sizes from pilot studies likely overestimate or underestimate the true effect size; rather we will determine empiric estimates from the control group as the basis for power calculations for a future multi-site trial.

For **Aim 3**, in order to explore an array of beliefs and practices regarding family contextual factors that promote or prevent effective SCA management, enrollment will continue until saturation is reached (i.e. more interviews will not generate additional information) in primary research questions. Based on our previous experience, we expect 25-35 parents will be sufficient to reach saturation.

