## Preliminary Studies

### **Family-centered approach for addressing SDoH for low-income children utilizing existing clinical infrastructure: the WE CARE Model.**

Our extensive groundwork has demonstrated that a family-

centered screening and referral intervention that relies on parental desire for assistance administered during pediatric preventive care visits led to increased provider referrals for, and parental receipt of, community resources. WE CARE (Well-Child care visit, Evaluation, Community Resources, Advocacy, Referral, Education) was efficacious in connecting families to community resources and resulted in

higher parental employment, receipt of fuel assistance and childcare, and lower odds of living in a homeless shelter, thereby reducing material need when tested in pediatric primary care clinics.

Ongoing work is providing a better understanding for the barriers (e.g., staff burden, lack of time and/or resources) and facilitators (e.g., clinic culture and leadership) for implementing this relatively simple intervention in general pediatric practice. This is necessary given the well-known challenge of incorporating efficacious innovations into routine medical practice. *Our WE CARE studies so far have focused on children without medically complex conditions and have been implemented only in primary care pediatric practices. Our studies to date have not been designed to measure the impact of WE CARE on child health outcomes, since they have targeted parents with healthy children.*

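### The cluster coefficient of 0.01 is stated as a ceiling for ED visits and penicillin adherence in hematology clinics, but the protocol supports it only from primary care studies of a different population

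*Combined protocol and SAP*

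**What the plan says.** Under Statistical Power and Sample Considerations, Aim 2 plans 35 families at each of four sites, two per arm. The clustering assumption is one clause: "based on our R00 WE CARE study, we expect a cluster coefficient no larger than 0.01". The same paragraph says "we expect at least 80% of children in our control group to have at least one ED visit" and expects at most 40% in the intervention group. It claims more than 90% power for a 25-point difference in ED visits. For penicillin adherence it expects 40% against 10% and claims 90% power for a 20-point difference. The only other test setting given is "Assuming a 5% error rate", without sidedness.

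Preliminary Studies describes where the earlier evidence comes from: "Our WE CARE studies so far have focused on children without medically complex conditions and have been implemented only in primary care pediatric practices". It adds "Our studies to date have not been designed to measure the impact of WE CARE on child health outcomes", and gives the reason: "since they have targeted parents with healthy children".

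The protocol does not say which outcome the 0.01 was estimated for, from how many clusters, or with what precision. It gives no argument for transferring the value and no sensitivity range.

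**The concern.** An intraclass correlation belongs to a particular outcome, population and type of cluster. By the protocol's own account, the source differs from the target on setting (primary care against hospital hematology) and population (children without complex conditions against children with SCA). The earlier studies were also not designed to measure effects on child health, which is what ED visits are used to reflect here. That the R00 study is one of these studies is an inference, because Preliminary Studies does not name it, but the section's wording covers all WE CARE work up to that point.

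The value is worded as a bound, not a best guess. With clusters of 35, each added 0.01 in the coefficient raises the design effect by 0.34, so the bound largely determines the stated power. At 80% prevalence, a coefficient of 0.01 means true site proportions vary with a standard deviation of √(0.01 × 0.80 × 0.20) = 4 points. At 0.05 it is √(0.05 × 0.16) = 8.9 points. The documents offer nothing to exclude the larger spread among four hospitals, and nothing to establish it either.

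**Working it through.** **Inputs from the power section.** Cluster size 35; 2 × 35 = 70 per arm; coefficient 0.01; 5% error; ED visits 80% (control) and 40% (expected, intervention); penicillin adherence 10% (control) and 40% (expected, intervention); detectable differences of 25 points (read as 80% against 55%) and 20 points (read as 10% against 30%).

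**Assumptions.** Two-sided test, no attrition, and all 70 per arm contributing to penicillin adherence. Eligibility is penicillin or hydroxyurea, so the real penicillin denominator may be smaller. Coefficients of 0.02 and 0.05 are illustrative; the documents give no value for SCA clinics.

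**Formulas.** Design effect DE = 1 + (35 − 1) × ICC. Effective n per arm = 70/DE. With p̄ the mean of the two proportions and d their difference,

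power = Φ{[d − 1.96 √(2p̄(1 − p̄)/n)] / √([p₁(1 − p₁) + p₂(1 − p₂)]/n)}.

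**The plan's own figures, at 0.01.** DE = 1.34 and n = 70/1.34 = 52.2.
- ED visits, 80% against 55%: p̄ = 0.675, the two standard errors are 0.0916 and 0.0883, and (0.25 − 1.96 × 0.0916)/0.0883 = 0.797. Power is 78.7%, against more than 90% stated. Unpooled variance gives 80.8%, arcsine 79.3% and a one-sided test 86.9%. Ignoring clustering altogether gives 89.3% (pooled) or 90.6% (unpooled).
- Penicillin, 10% against 30%: p̄ = 0.20, standard errors 0.0783 and 0.0758, and (0.20 − 1.96 × 0.0783)/0.0758 = 0.615. Power is 73.1%, against 90% stated.

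The stated figures are therefore not reproduced at the plan's own coefficient. That shortfall is separate from the choice of 0.01.

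**Sensitivity to the coefficient.**

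| | ICC 0.01 | ICC 0.02 | ICC 0.05 |
|---|---|---|---|
| Design effect | 1.34 | 1.68 | 2.70 |
| Effective n per arm | 52.2 | 41.7 | 25.9 |
| ED 80% vs 55%: power | 79% | 69% | 48% |
| ED: difference detectable with 90% power | 30 points | 33 points | 43 points |
| ED 80% vs 40% (expected): power | 99% | 97% | 86% |
| Penicillin 10% vs 30%: power | 73% | 63% | 43% |
| Penicillin: difference detectable with 90% power | 26 points | 30 points | 40 points |
| Penicillin 10% vs 40% (expected): power | 95% | 90% | 72% |

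For the expected 40-point ED effect, power stays at 90% or more up to a coefficient of about 0.041.

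**Number of clusters.** The table uses a normal reference. Four sites in two arms leave 4 − 2 = 2 degrees of freedom at cluster level. Using a noncentral t on 2 df with noncentrality d/√([p₁(1 − p₁) + p₂(1 − p₂)]/n), power at 0.01 is about 36% for 25 points and 66% for 40 points. The ED difference detectable with 90% power is then about 55 points at 0.01 and 68 points at 0.05.

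**The case against.** The best defence is that this is a pilot. The calculation is offered as a feasibility illustration, and the same section says the results will not be used to determine efficacy. The 0.01 is introduced as an expectation, which is a normal way to state a planning value. The expected ED effect is 40 points, and that remains well powered under the normal approximation even at 0.05. All of this stands, and it limits the weight of the point. It does not supply support for the ceiling or for the power stated at 25 points.

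Four stronger readings are tempting, and the documents do not carry them:
- **That 0.01 is wrong.** No coefficient for these outcomes in SCA clinics appears in the documents. A study not designed to measure child health effects may still have collected relevant data.
- **That no suitable estimate exists.** The documents show only that the protocol cites none.
- **That the borrowed coefficient is why the 25-point claim fails.** The claim already fails at 0.01. Only the further loss, from 79% to 69% or 48%, belongs to the coefficient, and it rests on assumed values.
- **That 0.01 will pass unexamined into the next trial.** The Data Analysis Plan commits to calculating the intraclass correlation, and the power section bases future calculations on empirical control-group estimates. This largely answers the worry.

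**Conclusion.** The protocol states an upper bound for the cluster coefficient that its own description of the earlier studies does not support for these outcomes and clinics. The finding is lack of support, not error in the value. Moving from 0.01 to an assumed 0.05 lowers power for a 25-point ED difference from 79% to 48% and raises the 90% detectable difference from 30 to 43 points. Power for the expected 40-point effect falls only from 99% to 86%. These figures assume full retention, a two-sided 5% test and a normal reference, and they are optimistic with two sites per arm. Severity is minor: no efficacy conclusion depends on the calculation.

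**What to change.** In Statistical Power and Sample Considerations, Aim 2:

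1. Replace the ceiling with a statement that 0.01 is a planning value borrowed from WE CARE work in primary care, and that the protocol cites no estimate for ED visits or penicillin adherence in hematology clinics. If the R00 value was estimated for a related outcome, name the outcome and give the number of clusters and the interval.
2. Replace the single power figures with the ranges tabulated above for coefficients of 0.01, 0.02 and 0.05, for both outcomes and including the expected 80% against 40% for ED visits. Label 0.02 and 0.05 as assumed.
3. State that these figures are optimistic because two sites per arm leave 2 degrees of freedom, and give the t-based 90% detectable ED difference: about 55 points at 0.01 and 68 points at 0.05.
4. Correct the power stated at 0.01 as a separate arithmetic matter.

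The cost is wording. The published figures become less favourable. No more families, visits or procedures are needed.

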emergency department visits as our primary outcome because it has been extensively, and commonly, used as a measure of lack of outpatient care and non-adherence to treatment regimens in this population. We will also calculate ED reliance (clinic visits kept / clinic visits kept + ED visits), as it has been used to discriminate frequent emergency department users.

Because qualitative research is by nature exploratory, we have not defined outcomes for the qualitative interviews with parents of children with SCA (**Aim 3**). Qualitative interviews will aim to examine parents' perceptions of factors that promote or hinder effective management of their child's SCA.

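### The stated power of more than 90% for a 25-point difference in ED visits is not assured: at the plan's own bounds for clustering and control rate it is about 79–81%

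*Combined protocol and SAP*

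**What the plan says.** All the inputs stand in the Aim 2 paragraph of Statistical Power and Sample Considerations.

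- **Sample:** four sites, two per arm, with 35 families at each, so 70 families per arm.
- **Error rate:** "Assuming a 5% error rate". Sidedness is not given.
- **Clustering:** "based on our R00 WE CARE study, we expect a cluster coefficient no larger than 0.01".
- **Control rate:** "we expect at least 80% of children in our control group to have at least one ED visit".
- **Expected intervention rate:** at most 40%, so an expected difference of at least 40 points.
- **Power claim:** "Our proposed study sample has >90% power to detect differences of at least 25% in the proportion of children with ED visits".

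The paragraph does not give the formula, any allowance for dropout, or whether the cluster coefficient entered the calculation. It closes with a pilot disclaimer: "we will not use results from this study to determine efficacy". Definition of Primary and Secondary Outcomes/Endpoints names "emergency department visits as our primary outcome", although the same section lists several groups of primary outcomes for Aim 2.

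**The concern.** A cluster coefficient of 0.01 looks negligible, but with 35 families per site it inflates the variance by about a third. The paragraph cites the coefficient just before the power figure, so a reader will assume that the figure allows for it. When a plan states an upper limit for clustering and a lower limit for the control rate, a power guarantee should hold at those limits. Here it does not.

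What is at stake is the smallest difference that the sample can detect reliably. Data Analysis Plan (Aim 2) foresees chi-square tests and mixed models between groups, so readers may lean on this sentence to interpret a null result for ED visits. The study also exists to supply parameters for a larger cluster trial, where the handling of clustering in the power calculation will matter.

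**Working it through.** **Inputs** (all from the Aim 2 paragraph): n = 70 per arm; m = 35 per site; ICC = 0.01 (upper bound); control rate p1 = 0.80 (lower bound); p2 = 0.80 − 0.25 = 0.55; α = 0.05. Two-sided testing is my default because the plan does not say.

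**Formulas.** Effective size per arm: n_eff = n / [1 + (m − 1) × ICC]. With d = p1 − p2 and p̄ = (p1 + p2)/2 = 0.675:

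- SE0 = √[2p̄(1 − p̄)/n_eff]
- SE1 = √{[p1(1 − p1) + p2(1 − p2)]/n_eff}
- Pooled power = Φ[(d − 1.96 × SE0)/SE1]
- Unpooled power = Φ[d/SE1 − 1.96]

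**Step 1: try to reproduce the stated figure.** With ICC = 0, n_eff = 70, SE0 = 0.0792 and SE1 = 0.0763.

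- Pooled: Φ[(0.25 − 0.1552)/0.0763] = Φ(1.24) = 89.3%
- Unpooled: Φ(3.277 − 1.960) = Φ(1.32) = 90.6%

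So at an 80% control rate, two-sided, more than 90% is reached only with the unpooled formula and almost no clustering (ICC up to about 0.0006). The pooled formula falls just short even at zero.

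**Step 2: apply the stated bound on clustering.** The design effect is 1 + 34 × 0.01 = 1.34, so n_eff = 70/1.34 = 52.2, SE0 = 0.0916 and SE1 = 0.0883.

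- Pooled: Φ[(0.25 − 0.1796)/0.0883] = Φ(0.80) = 78.7%
- Unpooled: Φ(2.831 − 1.960) = Φ(0.87) = 80.8%

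Other versions at the same bounds give 79.3% (arcsine), 71.9% (continuity-corrected) and 87–88% (one-sided, pooled to unpooled). None reaches 90%.

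**Step 3: vary the inputs** (25-point difference, 70 per arm, pooled to unpooled).

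| ICC | Control vs intervention | Two-sided power | One-sided power |
|---|---|---|---|
| 0 | 80% vs 55% | 89–91% | 94–95% |
| 0.001 | 80% vs 55% | 88–90% | 94% |
| 0.005 | 80% vs 55% | 84–86% | 91–92% |
| 0.01 | 80% vs 55% | 79–81% | 87–88% |
| 0.01 | 85% vs 60% | 83–85% | 90–91% |
| 0.01 | 90% vs 65% | 88–89% | 93–94% |
| 0.005 | 90% vs 65% | 92–93% | 96% |

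At ICC = 0.01, two-sided power reaches 90% from a control rate of about 91% (unpooled) or 92% (pooled). Placing the 25 points above the expected 40% instead (65% vs 40%) lowers power to 73–75% at ICC = 0.01.

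**Step 4: what the sample can detect.** At ICC = 0.01 and a control rate of 80%, solving for 90% two-sided power gives a difference of 28.7 (unpooled) to 29.6 (pooled) points. As a check, 80% vs 50% gives 91–92%. The expected 80% vs 40% gives about 99%.

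**Sensitivity, not a plan input.** The formulas use a normal reference, but there are only four sites. A site-level t-test with 2 degrees of freedom, at noncentrality 0.25/0.0883 = 2.83, would have about 36% power for 25 points.

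**The case against.** The strongest reply is that 0.01 and 80% are limits, and the plan never says that power was computed at both together. That is right, and the claim does hold in part of the stated range. Two-sided examples are ICC 0.005 with a 90% control rate (92–93%) and ICC 0.001 with 85% (91–92%). If the test is one-sided, power at an 80% control rate reaches 90% for coefficients up to about 0.006–0.0075, and at ICC 0.01 it does so from a control rate of about 83–85%. This rules out calling the sentence false under all of its assumptions. It does not rescue it: the plan specifies neither a one-sided test nor a control rate above its lower bound, and at that corner even one-sided power stays below 90%.

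A second reply is that the figure is illustrative. The paragraph uses ED visits as an example of feasibility, the pilot will not judge efficacy, the sample is presented as a field test, and the expected 40-point contrast is well powered by this method. This limits the consequence, but the printed number remains unsupported at the bounds.

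A third reply is that 79% is no floor either. That also stands: continuity correction gives 72%, a 2-df reference gives far less, and dropout would lower power further. Any replacement figure must name its method. Asking the plan to report power for a site-level test that it does not propose would be a preference rather than a correction.

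**Conclusion.** The concern holds. Power above 90% for a 25-point difference in ED visits is not assured by the assumptions cited for it. At the stated bounds it is about 79–81% two-sided (87–88% one-sided), and the difference detectable with 90% two-sided power is about 29–30 points. These figures assume 35 analysed families at every site with no dropout, a normal approximation and the usual design-effect formula. With only two sites per arm, that approximation is generous. The error is confined to the 25-point statement: the 80% versus 40% expectation is unaffected by this method, and no efficacy decision rests on the sentence. It should be corrected, but it does not threaten the study.

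**What to change.** Restate the sentence, naming its inputs. For example:

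> With 35 families per site, a cluster coefficient of 0.01 (design effect 1.34) and a control rate of 80%, two-sided 5% power by normal approximation is about 79% for a 25-point difference and about 91% for a 30-point difference. These figures assume no dropout and make no adjustment for having only two sites per arm.

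Both figures use the pooled variance. If the sponsor used a one-sided test, a smaller coefficient or a higher control rate, the sentence should say so and give the matching figure.

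An optional alternative that suits the pilot aim is to replace power with expected precision. At 80% versus 55%, the 95% confidence-interval half-width is 1.96 × 0.0883 = 17 points at a coefficient of 0.01, and 1.96 × 0.0763 = 15 points without clustering, again with a normal reference. A note that a site-level comparison would have much lower power would be useful but is not essential.

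The cost is a sentence or two of protocol wording, with no change to sample size, analysis or conduct. The stated power becomes less favourable.
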